12.5.9.2.1 Serious Adverse Events (Including Deaths)

A general summary table of Serious AEs will be presented by P3P variant and overall, including:

- The number of events and the number and percentage of subjects reporting at least one SAE, broken down by seriousness criteria (results in death, hospitalisation, life-

threatening, congenital anomaly/birth defect, disability/incapacity; important medical event);

- The number of events and the number and percentage of subjects reporting at least one SAE broken down by product relatedness (related, not related);
- The number of events and the number and percentage of subjects reporting at least one SAE broken down by study procedure relatedness (related, not related);
- The number of events and the number and percentage of subjects reporting at least one SAE broken down by expectedness (expected, not expected);
- The number of events and the number and percentage of subjects reporting at least one SAE broken down by severity, including a subject once with worst severity ;
- The number of events and the number and percentage of subjects reporting at least one SAE broken down by action taken related to the product (combining the following items: product use interrupted, product use reduced, product use stopped), treatment given and other action taken;
- The number of events and the number and percentage of subjects reporting at least one SAE leading to study discontinuation;

Additional summary tables of SAEs will be presented with a breakdown of the number of events, as well as the number and percentage of subjects reporting each AE, categorized by SOC and PT coded according to the MedDRA dictionary (version 22.0):

- The number of events and the number and percentage of subjects reporting at least one AE

SAEs will be listed in separate listings by P3P variant.

The data will be presented in the below outputs:

TFL number	Title
TABLES	
15.2.24.1	Summary of Serious Adverse Events – Safety Population
15.2.24.2	Summary of Serious Adverse Events by System Organ Class and Preferred Term – Safety Population
LISTINGS	
15.1.24.1	Listing of Serious Adverse Events

12.5.9.3 Investigational Product Events

All events relating to P3P Malfunction and Misuse will be listed for each subject, including event description and onset datetimes.

A summary table of P3P Product Events will be presented by P3P variant and overall, including:

- Number of P3P Product events and the number and percentage of subjects reporting at least one event.
- Number and percentage of subjects with device events linked to an AE

P3P Malfunction and Misuse events and inventory will be listed by P3P variant.

The data will be presented in the below outputs:

TFL number	Title
TABLES	
15.2.25.1	Summary of P3P Product events by Subject - Safety Population
15.2.25.2	Summary of P3P Product events by total number of P3P used – Safety Population
15.2.25.3	Summary of P3P Product events leading to an Adverse Event - Safety Population
LISTINGS	
15.1.25.1	Listing of P3P Events
15.1.25.2	Listing of AE related to P3P events

12.5.9.4 Clinical Laboratory Evaluation

Table 15 lists the hematology, clinical chemistry, and urine analysis parameters to be assessed in this study at Screening, Admission, Day 15, and Day 30.

Table 15: List of Laboratory Safety Parameters

Hematology	Clinical chemistry	Urine analysis
Hematocrit	Albumin	pH
Hemoglobin	Total protein	Bilirubin
Mean corpuscular hemoglobin	Alkaline phosphatase	Glucose
Mean corpuscular hemoglobin concentration	Alanine aminotransferase	Nitrite
Mean corpuscular volume	Aspartate aminotransferase	RBC traces
Platelet count	Blood urea nitrogen	Protein
Red blood cell (RBC) count	Creatinine	Specific gravity
White blood cell (WBC) count	Gamma-glutamyltransferase	
Differential WBC count:	Fasting glucose	
• Neutrophils	Lactate dehydrogenase	
• Basophils	Potassium	
• Eosinophils	Sodium	
• Lymphocytes	Total bilirubin	
• Monocytes	Direct bilirubin	
	Total cholesterol	
	Triglycerides	
	CRP (C-Reactive Protein)	

Any clinical safety laboratory test result that is outside of the normal reference range will be reviewed by the PI and assessed for clinical significance. If the PI considers the abnormal result to be of clinical significance, then it must be recorded as a concomitant disease at Screening, or if not present at Screening, as an AE during the study. If the condition worsens after screening it will be recorded as an AE. Abnormal laboratory test results detected at the Screening Visit whose Common Toxicity Criteria Adverse Event (CTCAE) grades are 2 or higher or still are CTCAE grade 1 and deemed clinically significant are usually concomitant disease or a manifestation of one and must be recorded accordingly. Abnormal laboratory test results detected after the Screening Visit whose CTCAE grades are 2 or higher or still are CTCAE grade 1 and deemed clinically significant must be either recorded as AEs or linked to a concomitant disease or still to an already reported AE.

The grading scheme used in the Common Terminology Criteria for Adverse Events and Common Toxicity Criteria [CTCAE] version 4.03) will be used by the PI to assess abnormal laboratory AEs.

Laboratory data will be summarized and listed at Screening, Day -1, Day 15 and at Day 30 or early termination, together with changes from baseline (last measurement obtained from screening or day -1 measurements). The number and percentage of subjects with:

- normal/low/high values
- clinical interpretation - normal, abnormal not clinically significant/abnormal clinically significant results)
- Severity - normal/abnormal laboratory findings by rating Mild, Moderate, Severe, Life Threatening based on CTCAE 4.0 grading

will be reported at Baseline Day 15 and at Day 30 or early termination, when appropriate.

Shift tables from Baseline for the normal/low/high values will be constructed at Day 15 and at Day 30.

Shift tables from Baseline over the product exposure (any visit post first product exposure) will be constructed for normal, abnormal not clinically significant/abnormal clinically significant results and for normal/abnormal laboratory findings by rating. For the shift table, the most "severe" value obtained during product exposure will be kept using the following order (from least severe to most severe):

Normal < Abnormal not clinically significant < Abnormal clinically significant

Normal < Mild < Moderate < Severe < Life threatening

Listings for the clinical laboratory data will include the following information: normal/high/low (with respect to the reference range), abnormal clinically relevant (as defined by

the PI), the change from baseline and the CTCAE grade. Only CTCAE grades equal or greater than one (Mild) will be presented.

The data will be presented in the below outputs:

TFL number	Title
TABLES	
15.2.26.1	Descriptive Statistics of Clinical Chemistry Parameters - Safety Population
15.2.26.2	Summary of Clinical Chemistry Parameters - Safety Population
15.2.26.3	Shift Table of Clinical Chemistry Parameters (Normal/Low/High) - Safety Population
15.2.26.4	Shift Table of Clinical Chemistry Parameters (Severity) - Safety Population
15.2.26.5	Shift Table of Clinical Chemistry Parameters (Clinical interpretation) - Safety Population
15.2.26.6	Descriptive Statistics of Hematology Parameters - Safety Population
15.2.26.7	Summary of Hematology Parameters - Safety Population
15.2.26.8	Shift Table of Hematology Parameters (Low/Normal/High) - Safety Population
15.2.26.9	Shift Table of Hematology Parameters (Severity) - Safety Population
15.2.26.10	Shift Table of Hematology Parameters (Clinical Interpretation) - Safety Population
15.2.26.11	Descriptive Statistics of Urinalysis Parameters - Safety Population
15.2.26.12	Summary of Urinalysis Parameters - Safety Population
15.2.26.13	Shift Table of Urinalysis Parameters (Normal/Low/High) - Safety Population
15.2.26.14	Shift Table of Urinalysis Parameters (Severity) - Safety Population
15.2.26.15	Shift Table of Urinalysis Parameters (Clinical Interpretation) - Safety Population
LISTINGS	
15.1.26.1	Listing of Clinical Chemistry Data, Shift, Changes from Baseline and CTCAE grades
15.1.26.2	Listing of Hematology Data, Shift, Changes from Baseline and CTCAE grades
15.1.26.3	Listing of Urinalysis Data, Shift, Changes from Baseline and CTCAE grades

12.5.9.5 Vital Signs, Physical Examination and Other Observations Related to Safety

12.5.9.5.1 Prior and Concomitant Medication

Prior medication is defined as any medication taken within 4 weeks prior to Screening. Any medication which was started prior to the Screening Visit and is still being taken by the subject will be considered as concomitant medication. Medication initiated after the Screening Visit is also referred to as concomitant medication.

All medications will be listed using PT and Anatomical Therapeutic and Chemical (ATC) codes (World Health Organization - Drug Dictionary Enhanced [WHO-DDE] March 2015 C format). A flag will be presented on the listing indicating whether the medication is prior or concomitant. Partial dates will not be imputed, but assumptions will be made as follows to assign to either prior or concomitant medications:

Date information	Assign as
Missing stop date	Concomitant
Partial date, e.g., --May2012, or ----2011. If month/year is the same as, or later than the month and/or year of Screening.	Concomitant
Partial date, e.g., --May2012, or ----2011. If month and/or year is earlier than the month and/or year of Screening.	Prior

Prior and Concomitant medications will be summarized for the Safety population (By Variant and Overall) showing the number (%) of subjects who used the medication at least once by sequence and by ATC 1st and 2nd levels medical term and by preferred drug name. Listings will display original dates (no imputation).

The data will be presented in the below outputs:

TFL number	Title
TABLES	
15.2.27.1	Summary of Prior Medication by Anatomical Therapeutic Classes (ATC) 1 and 2 – Safety Population
15.2.27.2	Summary of Prior Medication by Preferred Drug Name – Safety Population
15.2.27.3	Summary of Concomitant Medication by Anatomical Therapeutic Classes (ATC) 1 and 2 – Safety Population
15.2.27.4	Summary of Concomitant Medication by Preferred Drug Name – Safety Population
LISTINGS	
15.1.27.1	Listing of Prior and Concomitant Medication

12.5.9.5.2 Physical Examination

Physical examination data recorded during the study will be listed by P3P variant. Subject's data with abnormal and abnormal clinically significant physical examination findings will be flagged. Number of subjects (%) with normal, abnormal, and abnormal clinically significant results will be tabulated by body systems by visit.

Height recorded at the Screening visit and Body weight recorded at Screening visit, admission and discharge will also be listed. Descriptive statistics of body weight, and body height will be tabulated.

The data will be presented in the below outputs:

TFL number Title

TABLES

15.2.28.1	Summary of Weight and Height Measurements – Safety Population
15.2.28.2	Summary of Physical Examination of Body Systems – Safety Population
15.2.28.3	Shift Table of Physical Examination – Safety Population

LISTINGS

15.1.28.1	Listing of Physical Examination Findings, and Changes from Screening
-----------	--

12.5.9.5.3 Vital Signs

Systolic and diastolic blood pressure, pulse rate and respiratory rate measured during the study will be listed by P3P variant and study day.

Descriptive statistics will be presented for values and changes from baseline (baseline being the last measurement obtained prior to product test) and the number and percentage of subjects with normal/abnormal not clinically significant/abnormal clinically significant results will be reported by P3P variant and time point.

Shift tables from baseline over the product exposure (any visit post first product exposure) will be constructed for normal, abnormal not clinically significant/abnormal clinically significant vital signs results. For the shift table, the most "severe" value obtained during product exposure will be kept using the following order (from least severe to most severe):

Normal < Abnormal not clinically significant < Abnormal clinically significant

The data will be presented in the below outputs:

TFL number Title

TABLES

15.2.29.1	Descriptive Statistics of Vital Signs – Safety Population
15.2.29.2	Summary of Vital Signs – Safety Population
15.2.29.3	Shift Table of Vital Signs – Safety Population

TFL number Title

LISTINGS

15.1.29.1 Listing of Vital Signs Data and Changes from Baseline

12.5.9.5.4 Spirometry

Spirometry parameters assessed during the study include:

- Measured forced expiratory volume in 1 second (FEV₁)
- Measured forced vital capacity (FVC)
- FEV₁/FVC
- Percent of predicted FEV₁ (% pred)
- Percent of predicted FVC (% pred)
- FEF 25
- FEF 25 % predicted
- FEF 75
- FEF75 % predicted
- FEF 25-75
- FEF 25-75 % predicted

Measurement interpretation (categories: normal, abnormal not clinically significant, abnormal clinically significant) is collected by timepoint.

The above data are collected at all study day. At Screening, data are collected prior and post-bronchodilator, also including the brand (trade) name and dose of the bronchodilator.

At Day -1 spirometry will be performed before and after product use.

At Day 1 and 2 spirometry will be performed before product use and at the end of the daily product use.

Spirometry data values and normality evaluation will be listed by P3P variant and study day. Assessments performed after baseline will be listed together with change from baseline and shift in normality. Spirometry data from subjects who had significant clinical findings will be highlighted in listings.

Descriptive statistics will be presented for FEV₁, FEV₁ % predicted, FVC, FVC % predicted, FEF 25, FEF 25 % predicted, FEF 75, FEF75 % predicted, FEF 25-75, FEF 25-75 % predicted, FEV₁/FVC by study day by P3P variant. Spirometry data will be summarized together with changes from baseline (baseline being the last measurement obtained prior to product test), and the number and percentage of subjects with normal/abnormal/abnormal clinically significant results.

Shift tables from baseline over the product exposure (any visit post first product exposure) will be constructed for normal, abnormal not clinically significant/abnormal clinically significant spirometry results. For the shift table, the most “severe” value obtained during product exposure will be kept using the following order (from least severe to most severe):

Philip Morris Products S.A.

Statistical Analysis Plan

Confidential

Protocol P3P-SE-02-RU

Final v1.0 / 24 October 2019

Page 66 of 76

Normal < Abnormal not clinically significant < Abnormal clinically significant

The data will be presented in the below outputs:

TFL number	Title
TABLES	
15.2.30.1	Descriptive Statistics of Spirometry Results- Safety Population
15.2.30.2	Summary of Spirometry Results – Safety Population
15.2.30.3	Shift Table of Spirometry Results) – Safety Population
15.2.30.4	Descriptive Statistics of Spirometry Results- Safety Population – By Product Use Category
LISTINGS	
15.1.30.1	Listing of Spirometry Data and Changes from Baseline

12.5.9.5.5 Electrocardiogram

The ECG data will be obtained directly from the 12-lead ECG traces, i.e. not centrally read. These data include the PR, QT, and QT interval corrected using Bazett's formula (QTcB) and Fridericia's formula (QTcF) intervals; QRS duration; heart rate; and normality evaluation (normal, abnormal not clinically relevant, abnormal clinically relevant, together with any PI comments about the abnormality). ECG data values and normality evaluations will be listed by P3P variant and study day together with changes and shift in normality from baseline (Visit 2 Day -1). ECG data from subjects which had significant clinical findings will be highlighted in listings.

Descriptive statistics will be presented for ECG data at each study day by P3P variant and overall. ECG data will be summarized together with changes from baseline, and the number and percentage of subjects with normal/abnormal/abnormal clinical significant results.

A shift table for ECG assessments from baseline to worst assessment post-baseline, including unscheduled visits, will be done. For the shift table, the most "severe" value obtained during product exposure will be kept using the following order (from least severe to most severe):

Normal < Abnormal not clinically significant < Abnormal clinically significant

The data will be presented in the below outputs:

TFL number	Title
TABLES	
15.2.31.1	Descriptive Statistics of ECG Measurements - Safety Population
15.2.31.2	Summary of ECG Measurements – Safety Population
15.2.31.3	Shift of ECG Measurements(Normal/Abnormal no Clinically Significant /Abnormal Clinically Significant) – Safety Population
LISTINGS	

TFL number	Title
15.1.31.1	Listing of ECG Data and Changes from Baseline

12.5.9.5.6 Assessment of Cough

Cough questionnaire is assessed at Day -1, 2, 7, 15, 22, and 29. The number and % of subjects reporting a cough will be summarized by P3P variant. The responses to the individual items, including the VAS evaluating the level of cough bother and 3 Likert scales measuring the intensity, the frequency of cough and the amount of sputum production will be listed and summarized on each day by P3P variant, for all subjects who filled in the questionnaire.

The data will be presented in the below outputs:

TFL number	Title
TABLES	
15.2.32.1	Number and Percentage of Subjects with Cough – Safety Population
15.2.32.2	Summary of VAS Level Cough Bothersome by Timepoint – Safety Population
15.2.32.3	Summary of Intensity, Frequency of Cough and Sputum Production by Timepoint – Safety Population
LISTINGS	
15.1.32.1	Listing of Cough Assessment Results – VAS measurement
15.1.32.2	Listing of Cough Assessment Results - Frequency of Cough and Sputum Production

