### 7.7.6 Cough Assessment

At V2-V6, subjects will be asked if they have experienced a regular need to cough, e.g., whether they have coughed several times in the previous 24 hours prior to assessment. If the answer is 'yes', they will be asked to complete a cough assessment questionnaire (which includes a VAS and three Likert scales).

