### Confidentiality Statement

Data and information contained in this document are considered to constitute trade secrets and confidential commercial information, and the legal protections provided to such trade secrets and confidential information are hereby claimed under the provisions of applicable law. No part of this document may be publicly disclosed without the written consent of Philip Morris Products S.A.

	ECG	After resting for at least 10 min in supine position prior to recording.
	Body weight	
	Cough assessment	VAS and Likert
	Spirometry (without bronchodilator)	Has to be done at least 1 hour after smoking. After resting in sitting position for at least 15 minutes. To be done after vital signs and ECG.
Product test	Alternate use of P3P-1mg and P3P-2mg with up to 6 products in total	A wash-out period from any tobacco/nicotine containing products of at least 4 h prior to product test must be respected
After product test	Collection of used and unused products	
After product test and before randomization	Confirmation that subject is willing to use P3P during the study	
	Randomization	
	Vital signs	At least 5 min in supine position prior to measurement. At least 15 min after P3P use.
	Spirometry	To be done at least 1 hour after P3P use. After resting in sitting position for at least 15 minutes.
	Dinner	
Evening	Start of at least 10h nicotine wash-out period	
During the visit, after enrollment	Provide access and training for filling in questionnaires and product use diary	
During the visit, after enrollment	ABOUT™-Dependence questionnaire	
During the visit, after enrollment	Concomitant disease status check	Provide stop date if available
Ongoing	AE/SAE recording	
During product test	Product events malfunctions/misuse	

Abbreviations: ABOUT = Assessment of behavioral outcomes related to tobacco and nicotine products; AE = Adverse event; BoExp = Biomarkers of Exposure; ECG = Electrocardiogram; SAE = Serious adverse event; VAS = Visual analogue scale

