**Confidentiality Statement**

Data and information contained in this document are considered to constitute trade secrets and confidential commercial information, and the legal protections provided to such trade secrets and confidential information are hereby claimed under the provisions of applicable law. No part of this document may be publicly disclosed without the written consent of Philip Morris Products S.A.

Time	Blood Sample	Procedures	Additional Information
Start of Procedure		Day 1	
During/after product use		VAS-craving	Post T 0 , craving will be assessed at the following time points: 4 minutes (± 2 minutes) 10 minutes (± 2 minutes) 15 minutes (± 2 minutes) 30 minutes (± 5 minutes) 1 hour (± 10 minutes) 2 hours (± 10 minutes) 4 hours (± 10 minutes)
During product use		Puffing/inhalation behavior question	Assessment performed by site staff.
Within 60 min after product use		Collection and weighing of used product	
Within 60 min after product use		Questionnaires: - ABOUT™-product experience - Product acceptance - Sensory - Cough assessment	VAS and Likert
1 to 2 hours after T 0		Breakfast	
After the last blood collection for PK until 10:00 PM		On-site P3P use	Up to 14 P3P (15 in total including the one used for PK)
During the on-site product use period		Lunch and dinner	
After the end of daily product use		Vital signs	At least 5 min in supine position prior to measurement. At least 15 min after P3P use,
After the end of daily product use		ECG	After resting for at least 10 min in supine position.
1h after the end of daily product use		Spirometry	To be done at least 1 hour after P3P use. After resting in sitting position for at least 15 minutes. To be done after vital signs and ECG.
Ongoing		AE/SAE, concomitant medication recording	

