**Table 8 Time Schedule – Third day of V2 (Day 2)**

Time	Blood Sample	Procedures	Additional Information
Start of Procedure		Day 2	
Prior to product use		Vital signs	At least 5 min in supine position prior to measurement.
Prior to product use		Spirometry	After resting in sitting position for at least 15 minutes. To be done after vital signs.
6:30 AM - Discharge		On-site P3P use	Up to 15 P3P
During the visit		Puffing/inhalation behavior question	Answered by subjects.
Shortly before discharge		Vital signs	At least 5 min in supine position prior to measurement. At least 15 min after P3P use.
Shortly before discharge		Physical examination	
Shortly before discharge		ECG	After resting for at least 10 min in supine position.
Shortly before discharge		Spirometry	To be done at least 1 hour after P3P use. After resting in sitting position for at least 15 minutes. Done after vital signs and ECG.
At the end of the visit		Dispensing of P3P for ambulatory use	
After 6:30 PM		Discharge	
Ongoing		AE/SAE, concomitant medication recording	
Ongoing		Product events malfunctions/misuse	

**Abbreviations:** AE = Adverse event; ECG = Electrocardiogram; SAE = Serious adverse event

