#### Confidentiality Statement

Data and information contained in this document are considered to constitute trade secrets and confidential commercial information, and the legal protections provided to such trade secrets and confidential information are hereby claimed under the provisions of applicable law. No part of this document may be publicly disclosed without the written consent of Philip Morris Products S.A.

	Screening	Admission	Product use period (up to 15 products/day)					Discharge	Early termination	Safety Follow-Up
Visit	1		2		3	4	5	6		
Study day	-22 to -2	-1	1	2	7 ±2d	15 ±2d	22 ±2d	29 ±2d	30 ±2d	+14 days
Sensory Questionnaire			•						•	
VAS Craving p			•						•	
Puffing/inhalation behavior question (assessed by site staff)			•						•	
Puffing/inhalation behavior question (assessed by subject)				•	•	•	•			
Cough assessment (VAS, Likert scale)		•	•		•	•	•	•		
AE/SAE reporting	•	•	•	•	•	•	•	•	•	• q
Concomitant disease status		•			•	•	•			•
P3P product event reporting		•	•	•	•	•	•	•	•	

Abbreviations: ABOUT = Assessment of Behavioral Outcomes related to Tobacco and nicotine products; AE = Adverse event; B = Blood sample; BMI = Body mass index; BoExp = Biomarkers of Exposure; ECG = Electrocardiogram; PK = Pharmacokinetics; SAE = Serious adverse event; U = Urine sample; VAS = Visual analog scale

- a. Prior to enrollment, at Day -1 the following eligibility criteria will be re-checked: Inclusion criteria: smoking status confirmed by urine cotinine, subject is not planning to quit smoking within 2 months, subject is available for the entire study period and is willing to comply with the study procedures. Exclusion criteria: urine pregnancy test (all females), urine drug screen and alcohol breath test. The following eligibility criteria will only be checked at Day -1: Exclusion criteria: subject has received medication which has an impact on CYP2A6 activity within 14 days or within 5 half-lives of the drug prior to Day -1 (whichever is longer)
- b. Pre-study chest X-ray (with anterior-posterior and left lateral views). Available chest computed tomography (CT) or chest magnetic resonance imaging (MRI) results, or radiologist report from an equivalent radiological assessment within 6 months prior to Screening.
- c. Systolic and diastolic blood pressure, pulse rate, and respiratory rate. At V2 (Day -1, Day 1 and Day 2) and V6 (Day 30) vital signs are to be checked prior to any product use and at the end of the day/at discharge.

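### SAP 12.5.9.5.6 names Day 2 as a cough assessment day and leaves out Day 1, whereas the protocol schedules cough on Day 1 and not on Day 2

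*SAP*

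**What the plan says.** SAP 12.5.9.5.6 gives the timing: "Cough questionnaire is assessed at Day -1, 2, 7, 15, 22, and 29". It then provides that the VAS for cough bother and the three Likert scales will be "listed and summarized on each day by P3P variant, for all subjects who filled in the questionnaire". Three tables follow: 15.2.32.1 (number and percentage with cough), 15.2.32.2 (VAS by timepoint) and 15.2.32.3 (intensity, frequency and sputum by timepoint). Listings 15.1.32.1 and 15.1.32.2 are also planned.

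Protocol 7.7.6 is less specific: "At V2-V6, subjects will be asked if they have experienced a regular need to cough". It names no day within Visit 2 (Day -1, Day 1, Day 2) or Visit 6 (Day 29, Day 30). SAP 7.8.2 repeats it.

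The detailed protocol schedules do name the days. For Day 1, Table 7 includes cough among the items due within 60 minutes after the PK product: "Questionnaires: - ABOUT™-product experience - Product acceptance - Sensory - Cough assessment". Protocol Table 8, for Day 2, lists vital signs, spirometry, on-site use, the puffing question, physical examination, ECG, dispensing, and event and medication recording, but no cough item.

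**The concern.** Change from baseline in cough is a named safety endpoint (Protocol 3.2 and SAP 5.2, objective 4), and Protocol 2.3.3 lists cough among the foreseeable respiratory effects. P3P is an inhaled powder, and the study is about how users adapt to it over a month, so the earliest record after exposure is the natural start of the cough profile.

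The sentence with the wrong day sits in the analysis section, not in background text. SAP 12.1 restricts summary statistics to data detailed in the SAP, so an undetailed Day 1 is not brought back by a general rule. A programmer who follows the text would tabulate a day with no scheduled assessment and skip one that has it.

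The AE tables do not fully cover the gap. Protocol 7.7 says that symptoms reported on questionnaires need not also be recorded as AEs, on the ground that the questionnaires are themselves analysed. That reasoning works only if the questionnaires are summarised on the days when they are given.

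**Working it through.** No calculated figure is involved. The check sets the SAP day list beside the protocol schedules.

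| Day | Protocol source | Cough scheduled in protocol? | In SAP 12.5.9.5.6? |
|---|---|---|---|
| -1 | Table 6, before product test | Yes | Yes |
| 1 | Table 7, within 60 min after the PK product | Yes | **No** |
| 2 | Table 8 | No | **Yes** |
| 7, 15, 22 | Table 9 | Yes | Yes |
| 29 | Table 10, before wash-out | Yes | Yes |
| 30 | Table 11 | No | No |

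1. **Appendix A.** The cough row of the protocol's Appendix A agrees with the tables: marked at Day -1, 1, 7, 15, 22 and 29, and blank at Day 2 and Day 30. The text I could read of the SAP's own Appendix A does not show its cough row, so the comparison rests on the protocol.

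2. **Set comparison.** The protocol has {-1, 1, 7, 15, 22, 29} and the SAP has {-1, 2, 7, 15, 22, 29}. Each has six days, five of them shared. Only Day 1 is in the protocol alone, and only Day 2 in the SAP alone.

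3. **Is it a declared change?** SAP section 9 lists changes of analysis population, the dropping of most combined-variant results, and changes of model for PK and craving. It says nothing about cough days.

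4. **Likely origin.** The sequence 2, 7, 15, 22, 29 is the set of days on which subjects answer the puffing/inhalation question (SAP 5.2, objective 2). A copying slip is a reasonable inference, but only that.

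5. **What the summaries would lack.** Of the five scheduled post-baseline cough days (1, 7, 15, 22, 29), four would be summarised. The first of those is Visit 3, on Day 7 with a window of ±2 days, that is, Day 5 to Day 9. The question looks back 24 hours, so no planned by-day summary would reach the product test, the first randomized use or the first days of use.

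6. **What Day 1 measures.** The Day 1 answer also looks back 24 hours. The product test on Day -1, with up to six products alternating between variants, ends at least 10 hours before the PK product is started. The Day 1 record therefore ordinarily covers that test as well as the single randomized product.

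7. **Which tables.** The explicit by-day wording governs the VAS and Likert items (15.2.32.2 and 15.2.32.3). Applying the same days to 15.2.32.1 is the natural reading, but the text does not say so.

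**The case against.** The case for leaving this alone, or treating it as trivial, has several parts.

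- **Nothing disappears from the record.** SAP 12.1 calls for listings of all data collected, and two cough listings are planned. This stands. A reader might infer that the early tolerability data are lost; the documents support only their absence from the planned by-day summaries.
- **Other early safety data exist.** AEs are recorded throughout Day -1 and Day 1, Protocol 12.6.3 makes AEs the primary safety assessment, and spirometry is done before and after use on Day 1. This stands, subject to the Protocol 7.7 provision on questionnaire symptoms.
- **Day 1 is not a clean reading of one product.** A reader might take it as a measure of cough caused by a single supervised use, because it is taken within an hour of that use. The 24-hour recall rules this out, and since both variants are tried on Day -1, the Day 1 comparison between variants is blurred.
- **The number affected is smaller than it may look.** About 60 randomized subjects might be inferred for every table. Only those who answer yes to the cough question complete the VAS and Likert scales, so that figure can apply at most to the yes/no item.
- **Omission is not certain.** The sentence states when cough is assessed, not what is excluded. SAP Table 8 already has a Day 1 label, and the TFL shells are a separate document. This stands in part: the shells may be right, but the SAP text would still be wrong.
- **The eCRF may differ.** The SAP cites eCRF version 4.0, which is not available here, and the general reference to Visits 2 to 6 does not exclude Day 2. This stands as a reason to check before correcting. If the eCRF does collect cough on Day 2, the SAP and the protocol schedule still conflict.

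Protocol 4.1 and SAP 6.1 also say that Day 30 repeats the Day 1 assessments, which could suggest a Day 30 cough assessment. Table 11, the protocol's Appendix A and the SAP's own day list do not include one.

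**Conclusion.** The SAP day list is wrong as written against the protocol: Day 2 appears in place of Day 1, with no declared change. If it is followed, one of five scheduled post-baseline cough days, the first after P3P exposure, is left out of the planned by-day summaries, and one entry has no scheduled data.

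The point is minor. The endpoint is descriptive and secondary, no test depends on it, no cough table is in the topline set, and the primary PK analysis is unaffected. The conclusion assumes that the detailed protocol schedules govern the assessment days and that the eCRF follows them. The documents do not show that any data would go uncollected or unlisted.

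**What to change.** Check the day list in SAP 12.5.9.5.6 against the protocol schedule and the eCRF, correct it to Day -1, 1, 7, 15, 22 and 29, and align the TFL shells for 15.2.32.1 to 15.2.32.3. SAP Table 8 needs no change. If the eCRF turns out to place cough on Day 2, record that difference from the protocol schedule in SAP section 9 and reconcile the documents before database lock.

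A sentence alongside the tables noting that the Day 1 answer spans the Day -1 product test of both variants would help the reader of the report.

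The cost is one number in the SAP and a check of the eCRF and shells. No new table is needed, and no new data if the eCRF follows the protocol.
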